We will recruit up to 10 subjects with a goal of 8 completers. Study candidates will be screened for inclusion and exclusion criteria by any member of the study team. Those who meet criteria and consent to the study will be enrolled. If no consent provided, the patient will not be enrolled and the reason for their non-participation included with the date of screening.

Eligibility Criteria

Inclusion Criteria

- Provide consent to participate in the study
- Individuals of either sex, 21-85~~9~~ years of age
- Clinically defined Restless Leg Syndrome, and problematic augmentation currently on dopaminergic treatment.
- Subjects with reproductive capability including all males and women of child-bearing potential (WOCBP) must agree to practice continuous abstinence or adequate contraception methods (appropriate double barrier method or oral, patch, implant, or injectable contraception) from as soon as feasible during screening period until at least 30 days after the last dose (i.e., intermittent abstinence based on “rhythm”, temperature monitoring, or other means of timing is not acceptable)

Exclusion Criteria

- Current use of Opioid medications
- Clinical relevant depression or other medical problems that in the opinion of the investigator would not allow for safe completion of the protocol.
- Suicidal ideation
- History of epilepsy
- Current MAO inhibitors
- History of hepatic or renal impairment
- Women who are pregnant or breastfeeding

Study Procedures

Our aim is to determine the mechanism of dopaminergic induced augmentation and if a D1 antagonist drug can improve augmentation symptoms. Subjects will be randomized to Ecopipam or placebo for 5 weeks/arm in two periods with a 2-week washout period in between. Total time for subject participation is

approximately 13 weeks.

Medical History

The history will center on risk factors and symptoms or disorders relevant to neurological disorders.

Physical and Neurological Examinations

Brief standard neurological examinations will be done similar to that of a normal clinic visit. Laboratory assessments of serum chemistry and a 12-lead ECG will be conducted on the first day (before initiating treatment) and the last day of treatment of each crossover phase (i.e. Ecopipam or placebo).

At each Visit subjects will undergo:

- Verification of continued trial participation
- Assessment of overall wellness with query for adverse events and safety reporting

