- Clinical Global Impressions and safety calls at week 1 and 3 of each arm, and 1 week after withdrawal) of each arm.
- Completion of following instruments:
 - International RLS Rating Scale,
 - Augmentation Severity Rating Scale,
 - Epworth Sleep Scale,
 - Hamilton Depression Scale,
 - MOS Sleep Scale,
 - Fatigue Severity Scale, and
 - Montreal Cognitive Assessment
 - Columbia Suicide Assessment Scale.
 - Vital signs and examination
- Education on and/or review of the 24-hour RLS Symptom diary to be kept just prior to starting each arm and just before ending each arm. Analysis will be last observation carried forward.

Concurrent Medications for RLS

The following medications are allowed dopamine agonists (pramipexole, ropinirole, rotigotine)
The following medications are prohibited: dopamine antagonists, anti-histaminergic medications. In addition, Ecopipam has been shown a competitive inhibitor for CYP2D6 at nanomolar concentrations, and as such, the use of strong CYP2D6 inhibitors (i.e. Fluoxetine, Paroxetine, Bupropion, Quinidine, Cinacalcet and ritonavir) are prohibited.

Schedule of Events:

Study procedures (Per patient)	Baseline Screening Visit: Day -14 to 0	Visit 1: Day 0	Phone Call 1: Day 8	Visit 2: Day 15	Phone Call 2: Day 22	Visit 3: Day 36	Phone Call 3: Day 43	Visit 4: Day 50	Phone Call 4: Day 57	Visit 5: Day 65	Phone Call 5: Day 72	Visit 6: Day 84	Phone Call 6: Day 91
Informed consent	X												
Inclusion/exclusion criteria	X												
Demographic data	X												
Medical history	X												
Prior and/or concomitant medication review	X	X	X	X	X	X	X	X	X	X	X	X	X
Physical examination/Neurological exam	X			X		X		X		X		X	
Vital signs	X			X		X		X		X		X	
12-Lead ECG	X					X						X	
Urine pregnancy test (WOCBP)	X					X						X	
Serum Chemistry	X					X						X	
International RLS Rating Scale (IRLS Scale)		X		X		X		X		X		X	
Body weight and height		X		X		X		X		X		X	
Augmentation Severity Rating Scale	X	X		X		X		X		X		X	
Epworth Sleep Scale		X		X		X		X		X		X	
Hamilton Depression Scale		X		X		X		X		X		X	
MOS Sleep Scale		X		X		X		X		X		X	
Montreal Cognitive Assessment (MoCA)		X		X		X		X		X		X	
Fatigue Severity Scale		X		X		X		X		X		X	
Columbia-Suicide Severity Rating Scale (C-SSRS)		X		X		X		X		X		X	
Clinical Global Impressions (CGI)		X	X	X	X	X	X	X	X	X	X	X	X
Dispense 24-hour RLS Symptom diary	X							X					
Review of 24-hour RLS symptom diary		X		X		X		X		X		X	
Study drug dispensation		X						X					
Adverse Events		X	X	X	X	X	X	X	X	X	X	X	X

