Investigational Product

Ecopipam (also known as PSYRX 101 or SCH 39166) hydrochloride is a potent, selective antagonist of human D1 and D5 dopamine receptors. Dopamine is a neurotransmitter in the central nervous system, and its receptors have been classified into two “families” based on their genetic structure: “D1” (including subtypes D1 and D5) and “D2” (including subtypes D2, D3 and D4). D1-receptor super-sensitivity may be a mechanism for the repetitive and compulsive self-injurious behaviors. Ecopipam is a selective antagonist of the D1-receptor family and had been investigated for the symptomatic relief of self-injurious behavior (SIB) in patients with Lesch-Nyhan Disease, Pathological Gambling and Tourette Syndrome. Detailed information about ecopipam development may be found in the Investigator Brochure.

Subjects will be randomized in a double-blind fashion to study drug: ecopipam or matching placebo, supplied by Psyadon Pharmaceutical for study period 1 and 2. Prior to drug dispensation to subjects, subjects will be provided a diary, instructed on daily morning dosing, and asked to return all unused drug and packaging with the diary to the clinic. Subjects will be instructed to report any concerns and/or side effects on contact calls that will occur between study visits.

The double-blind drug assignment code will be maintained in a confidential manner where investigator, study team and patients are unaware of individual treatment assignments. Randomization process must be completed by research personnel not involved in conduct of study visits. Only in the event of a subject related emergency with the specific request to unblind the study drug by the Principal Investigator will the identity of the double-blind drug will be disclosed.

Subjects will be seen six times to complete the study. Arm1 baseline/screening, Arm 1 week 3, Arm 1 week 5, Arm 2 baseline, Arm 2 week 3, Arm 2 week 5. Once daily morning dosing will occur for 5 weeks per arm with weekly dose escalation as the example shows below:

Study Period 1

- Ecopipam or matching placebo 25 mg by mouth for 7 days (week 1), followed by
- Ecopipam or matching placebo 50 mg by mouth for 7 days (week 2), followed by
- Ecopipam or matching placebo 100 mg by mouth for 23 days (weeks 3).
- Wash-out for 2 weeks to allow subjects to switch study arms.

Study Period 2

- Matching placebo or ecopipam 25 mg by mouth for 7 days (week 7), followed by

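### The dose steps add to 37 days per arm against a stated 5 weeks (35 days), and the end-of-treatment visits and withdrawal calls are spaced two days differently in the two periods

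*Protocol*

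**What the plan says.** **Arm length.** Protocol, Study Procedures: "Subjects will be randomized to Ecopipam or placebo for 5 weeks/arm in two periods with a 2-week washout period in between". The Investigational Product section repeats the 5 weeks as once-daily morning dosing and presents the dose steps as an example of the escalation. Total participation is given as "approximately 13 weeks".

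**Dose steps.** Under Study Period 1: 25 mg for 7 days, 50 mg for 7 days, then "Ecopipam or matching placebo 100 mg by mouth for 23 days (weeks 3". Study Period 2 has the same three durations, labelled weeks 7, 8 and 9.

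**Timing rules.** Physical and Neurological Examinations puts chemistry and ECG on the first day, before treatment, and on "the last day of treatment of each crossover phase (i.e. Ecopipam or placebo". The list of visit procedures calls for "safety calls at week 1 and 3 of each arm, and 1 week after withdrawal".

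**Visit table (Schedule of Events).** Drug is dispensed at Visit 1 (Day 0) and Visit 4 (Day 50). ECG and chemistry are ticked at Visit 3 (Day 36) and Visit 6 (Day 84). The calls that follow are "Phone Call 3: Day 43" and "Phone Call 6: Day 91".

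Subjects are "asked to return all unused drug and packaging with the diary to the clinic", but no visit is named for the return. The protocol does not say whether the first dose is taken on the dispensing day or the next morning.

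**The concern.** The duration statement and the list it introduces disagree by two days, and both bear on how the trial is run. Kits are packed per participant to the protocol's requirements, so the packager must know whether an arm has 21 or 23 doses at 100 mg. The visit table does not settle the matter, because its own spacing differs by two days between periods.

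Two things depend on this. The first is the end-of-treatment safety picture: if dosing runs past the end visit, the last ECG, chemistry and C-SSRS miss the final doses. The second is the withdrawal observation. The synopsis says a cross-over was chosen over an open-label study specifically to document removal of the drug under blind, so a withdrawal call that falls at different times after the last dose in the two periods touches the stated purpose of the design.

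**Working it through.** **1. Arm length.** Stated: 5 × 7 = 35 days. Dose steps: 7 + 7 + 23 = 37 days in each period. The difference is 2 days and depends on no counting convention. With 21 days at 100 mg the sum is 7 + 7 + 21 = 35.

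**2. Spacing in the visit table** (days after the dispensing visit):

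| Contact in the period | Period 1 (from Day 0) | Period 2 (from Day 50) |
|---|---|---|
| First call | 8 | 57 − 50 = 7 |
| Mid visit | 15 | 65 − 50 = 15 |
| Second call | 22 | 72 − 50 = 22 |
| End visit | 36 | 84 − 50 = 34 |
| Withdrawal call | 43 | 91 − 50 = 41 |

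**3. Can the timing rules be met in both periods?** Let the first dose come f days after dispensing and the arm have n daily doses. The last dose is then f + n − 1 days after dispensing. An end visit on the last dosing day needs f + n − 1 = 36 in Period 1 and 34 in Period 2. A call 7 days later needs f + n − 1 + 7 = 43 and 41, which is the same pair of conditions. No single f and n satisfies both.

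**4. What each reading gives:**

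| First dose (P1 / P2) | Doses per arm | Last dose (P1 / P2) | Visit 3 | Visit 6 | Calls 3 / 6, days after last dose | Dose-free days between |
|---|---|---|---|---|---|---|
| Day 0 / 50 | 37 | 36 / 86 | on last dose | 2 doses still to come | 7 / 5 | 13 |
| Day 0 / 50 | 35 | 34 / 84 | 2 days after | on last dose | 9 / 7 | 15 |
| Day 1 / 51 | 37 | 37 / 87 | 1 dose to come | 3 doses to come | 6 / 4 | 13 |
| Day 1 / 51 | 35 | 35 / 85 | 1 day after | 1 dose to come | 8 / 6 | 15 |
| Day 1 / 50 (mixed rule) | 35 | 35 / 84 | 1 day after | on last dose | 8 / 7 | 14 |

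The first four rows use one first-dose rule, and in each the periods differ by 2 days. The last row uses a different rule in each period.

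**5. Stopping at the end visit.** With dosing on both the dispensing day and the end-visit day, the arms have 36 − 0 + 1 = 37 and 84 − 50 + 1 = 35 doses. Nominal totals are 7×25 + 7×50 + 23×100 = 2,825 mg and 7×25 + 7×50 + 21×100 = 2,625 mg, a ratio of 1.076. With the first dose the next morning, the counts are 36 and 34.

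**6. Off-drug interval.** The protocol gives a half-life of 8–15 hours. Two days is 48/15 = 3.2 to 48/8 = 6 half-lives.

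**7. Total duration.** 35 + 14 + 35 + 7 = 91 days = 13.0 weeks; 37 + 14 + 37 + 7 = 95 days = 13.6 weeks.

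**The case against.** The strongest reply is that the table is nearly right and only the 23 is a slip. Five weeks is stated twice as the rule, while the step list is called an example. If Day 0 is dispensing and Day 1 the first dose, every later Period 1 contact, and Visit 4, is Day 1 plus whole weeks: Days 8, 15, 22, 36, 43 and 50. The same grid in Period 2 would give 57, 64, 71, 85 and 92, against 57, 65, 72, 84 and 91 in the table, so Period 2 would simply have one-day slips. Dosing on Days 1–35 and 50–84 also gives 35 days in both periods with 14 dose-free days.

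Much of this stands. A reader might infer that the table fixes 37 dosing days in Period 1 and 35 in Period 2, or that no single arm length can fit. The documents do not support either: those counts require a dose on both the dispensing day and the end-visit day, which the protocol does not state, and 35 days does fit under the mixed rule. Nor can one say that only Period 2 agrees with 5 weeks, since the Day 1 grid makes Period 1 the regular one.

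The reply does not remove the problem. The mixed rule starts dosing the day after dispensing in one period and on the dispensing day in the other. It still leaves Visit 3 one day after the last dose, against the last-day-of-treatment rule. Calling the list an example does not help either, because no other regimen is given. The protocol states no visit windows, and a window would not say how many doses to pack.

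The return of unused drug makes dosing beyond Visit 6 less likely if it is applied at that visit. Dose reduction is allowed, so the milligram totals in step 5 are nominal.

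**Conclusion.** The point holds as a minor inconsistency. Two facts are firm: the dose steps exceed the stated arm length by 2 days in both periods, and the end visits and withdrawal calls are spaced 2 days differently between periods. It follows, for any one first-dose rule and arm length, that the table cannot meet the last-day-of-treatment rule or the one-week-after-withdrawal rule in both periods. Which period is misplaced cannot be determined. The approximate 13-week total sits better with 35-day arms but does not prove them.

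The consequences depend on which line the site follows:

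- If 37 days are dosed from Day 50, two 100 mg doses (of ecopipam or placebo) follow the final ECG, chemistry and C-SSRS, and Call 6 comes 5 days after the last dose instead of 7.
- If 35 days are dosed from Day 0, Visit 3 falls two days after the last dose while Visit 6 falls on it.

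In the second case a reader might assume that two days cannot matter to the ratings. At the stated half-life that gap is about 3 to 6 half-lives, so an effect on the Period 1 end-of-treatment ratings cannot be dismissed. The protocol gives no basis for sizing it. This remains a small timing fault in an exploratory study of up to 10 subjects and does not undermine the design.

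**What to change.** Assuming 5 weeks is intended:

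- Change the 100 mg step from 23 to 21 days in both periods.
- Number Visit 1 as Day 1 and state that the first dose of each period is taken on the dispensing day. Dosing is then Days 1–35 and 50–84, with 14 dose-free days (36–49).
- Move Visit 3 to Day 35, Call 3 to Day 42, Visit 5 to Day 64 and Call 5 to Day 71. Leave the other contacts where they are.
- Correct the week labels: 100 mg in weeks 3–5 of Period 1; in Period 2, 25 mg in week 8, 50 mg in week 9 and 100 mg in weeks 10–12.

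The contacts then fall 7, 14, 21, 34 and 41 days after dispensing in both periods. Each end visit is on the last dosing day and each withdrawal call is 7 days later.

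If 37 days is intended, restate the arm length and shift Visit 4 and everything after it. Dose Days 0–36, leave Days 37–50 dose-free, and set Visit 4 to Day 51, Call 4 to Day 59, Visit 5 to Day 66, Call 5 to Day 73, Visit 6 to Day 87 and Call 6 to Day 94. Both periods then have offsets of 8, 15, 22, 36 and 43 days.

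Either way the cost is an amendment to the wording and the visit table, with no added subjects, visits or assessments.

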CLINICAL STUDY PROTOCOL

Study Title: **Treatment of Restless Leg Syndrome (RLS) Augmentation with Ecopipam, a D1 Specific Antagonist**

Sponsors: Houston Methodist Research Institute (HMRI)
[name].

IND #: 132835

Principal Investigator: [name].
Director of Movement Disorders Clinic
Houston Methodist Neurological Institute (HMNI)
Houston Methodist Research Institutes (HMRI)
Houston Methodist Hospital

Medical Emergencies: [name].
[contact]
Mobile [contact]

Protocol Version: V4.0 - 09.25.17

[name].
Principal Investigator/Sponsor-Investigator
Director, Movement Disorders
Houston Methodist Neurological and
Research Institutes
[name]
[name]
[contact]

Date

Table of Contents

STUDY SYNOPSIS	3
BACKGROUND AND RATIONALE FOR THE OBJECTIVES	3
STUDY AIMS/OBJECTIVES	3
STUDY DESIGN	4
PROCEDURES	
Protection of Human Subjects	5
Informed Consent and HIPAA Compliance	5
Potential Risks and Benefits	6
Statement of Non-Participation	6
Patient Confidentiality (HIPAA)	6
Eligibility (Inclusion/Exclusion Criteria)	8 7
Study Procedures	8 7-8
Schedule of Events	8
Investigational Product	8-9
Event Monitoring of Subjects	10
Data Management and Storage	11
Reporting of Study Findings	15 14
Participant Compensation	15 14
REFERENCES	12
ATTACHMENTS 1-10	13-23

STUDY SYNOPSIS

This is an exploratory study, the first ever designed specifically to treat augmentation, designed to assess gross tolerability and obtain data for a power analysis and other study design features in subsequent studies, if a signal is detected. A cross-over design was selected over an open label study specifically to blindly document the effect of D1 antagonist removal. It is not at all known if there will be a carry-over effect, immediate return of symptoms, rebound exacerbation, etc. Future studies could assess the ability to discontinue the D2 agonist, the ability to prevent augmentation in DA treated patients, and the assessment of a D1 antagonist to treat de novo RLS.

Project specific aim: (1) To determine the mechanism of dopaminergic induced augmentation and if a D1 antagonist drug can improve augmentation symptoms.

Background and Rationale for the Objectives

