During the study, the Investigator and study team will be responsible for monitoring, collecting, following-up on, and reporting AEs and SAEs, as detailed in this section of the protocol. Adverse events will be reported by the subject (or, when appropriate, by a caregiver, surrogate, or the subject's legally acceptable representative) according to the definition below. Only adverse events associated with the research component of trial participation will be captured, examples include but are not limited to: somnolence, headache, insomnia.

The stopping rules for this trial will be determined by the Sponsor Investigator, Houston Methodist Hospital &/or Houston Methodist Research Institute, and/or HMRI Institutional Review Board. The Principal Investigator may withdraw a subject for their safety and welfare. Participants will be withdrawn at either 3x ULN for AST/ALT, kidney function changes from baseline as determined by BUN/Creatinine or when unintended pregnancy occurs.

Event Monitoring Definitions

Adverse Event (AE): An adverse event (AE) is any untoward medical occurrence associated with the use of a drug in humans, whether or not considered drug related. An adverse event can therefore be any unfavorable and unintended sign (including an abnormal laboratory finding), symptom, or disease temporally associated with the use of a drug and does not imply any judgment about causality. An adverse event can arise with use of any drug or medicinal product. AEs are to be reported to the IRB per IRB policy and to the sponsor at the time of annual reporting.

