Serious Adverse Event (SAE): A serious adverse event (SAE) is any untoward medical occurrence that occurs irrespective of study treatment assignment, if it satisfies any of these criteria: results in death; is life-threatening; requires inpatient hospitalization or prolongs existing hospitalization; results in persistent or significant disability or incapacity or substantial disruption of the ability to conduct normal life functions; or if the event is a congenital anomaly or birth defect. Important medical events that may not result in death, be life-threatening, or require hospitalization may be considered serious when, based upon appropriate medical judgment, they may jeopardize the patient or subject and may require medical or surgical intervention to prevent one of the outcomes listed in this definition. SAEs are to be reported to the IRB per IRB policy and to the sponsor at the time of IRB reporting for further reporting to the FDA.

Assessment of Intensity: The Investigator will make an assessment of intensity for each AE and SAE reported during the study. The assessment will be based on the Investigator's clinical judgment. The intensity of each AE and SAE recorded in the subject record should be assigned to one of the following categories:

- Mild: An event that is easily tolerated by the subject, causing minimal discomfort and not interfering with everyday activities.
- Moderate: An event that is sufficiently discomforting to interfere with normal everyday activities.
- Severe: An event that prevents normal everyday activities.

Relationship to Study Drug - Assessment of Causality: The Investigator is obligated to assess the relationship between study drug and the occurrence of each AE/SAE. The Investigator will use clinical judgment to determine the relationship. Alternative causes, such as natural history of the underlying diseases, concomitant therapy, other risk factors, and the temporal relationship of the event to the study drug will be considered and investigated. The Investigator will assess causality based on the following definitions:

- Not Related (the AE was more likely explained by causes other than the study treatment).
- Related (the study treatment and AE were closely related in time and the AE may be explained by exposure to study product: e.g., known pharmacological effect or recurrence on re-challenge).

Participant Compensation

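### The rule on which adverse events are captured conflicts with the protocol's own AE definition and causality step, and as written it would under-record AEs in a tolerability study

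*Protocol*

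**What the plan says.** The opening paragraph of Safety Monitoring of Subjects (Protocol) makes the investigator and study team responsible for AEs and SAEs and says that AEs are reported "according to the definition below". The next sentence narrows this: "Only adverse events associated with the research component of trial participation will be captured". It adds that "examples include but are not limited to: somnolence, headache, insomnia".

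Under Event Monitoring Definitions, an AE is "any untoward medical occurrence associated with the use of a drug in humans, whether or not considered drug related". The same definition goes on to include any unfavourable sign, symptom or disease "temporally associated with the use of a drug and does not imply any judgment about causality".

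Under Relationship to Study Drug, "The Investigator is obligated to assess the relationship between study drug and the occurrence of each AE/SAE". Alternative explanations, such as the course of the underlying disease or concomitant therapy, are to be weighed at that step. One of the two outcomes is "Not Related (the AE was more likely explained by causes other than the study treatment".

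The Study Synopsis describes the trial as "designed to assess gross tolerability". The section on potential risks states that ecopipam's effect on RLS at start and at discontinuation is unknown.

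**The concern.** The capture sentence puts a judgment about attribution before recording. The definition and the causality section put recording first and attribution second. Staff cannot follow both when they think an event is unrelated to the research.

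The order matters because the placebo period allows event frequencies to be compared without an opinion on each event's cause. An event screened out at entry is lost to that comparison, and a later analysis plan cannot restore to the AE data what was never entered. The safety analysis planned after five enrolled subjects would draw on the same record.

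The events most easily put down to other causes are those that resemble the underlying disease or an ordinary illness. The synopsis lists carry-over, return of symptoms and rebound as open questions, so disease-like events are of direct interest. All three examples in the capture rule also appear in the risk section as known effects, which may steer staff towards what is already expected.

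**Working it through.** The protocol gives no figure on this point and has no power analysis, so there is none to reproduce. The check is first textual, then an illustration of scale.

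**The texts side by side**

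| Question | Capture sentence | AE definition and causality section |
|---|---|---|
| What qualifies an event? | Association with the research component | Untoward occurrence, linked in time to drug use |
| Is attribution needed to record it? | Yes, as written | No; the definition disclaims any such judgment |
| When is cause considered? | Before recording | After recording, for each AE and SAE |
| What of events with another likely cause? | May be left out | Recorded, then classed as not related |

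An intercurrent infection in week 4 is an example. Under the definition it is an AE, to be graded and assessed for cause. Under the capture sentence it can be left out because it does not seem to come from the research.

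**Illustration of scale**

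Inputs: n = 10 exposed subjects, the planned maximum; n = 8, the goal for completers; capture fraction c = 1, 0.7 or 0.5. The values below 1 are assumptions with no source in the documents. Subjects are taken as independent, with at most one event of a given type each, and c as the same for every event of that type.

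With zero recorded events, the one-sided 95% upper limit on the recorded rate is U = 1 − 0.05^(1/n). The recorded rate is c × p, so the limit on the true rate p is U / c.

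- n = 10, c = 1: 1 − 0.05^(1/10) = 0.259, or 26%
- n = 10, c = 0.7: 0.259 / 0.7 = 0.370, or 37%
- n = 10, c = 0.5: 0.259 / 0.5 = 0.518, or 52%
- n = 8, c = 1: 1 − 0.05^(1/8) = 0.312, or 31%

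Seen the other way, the chance of recording at least one event is 1 − (1 − c × p)^n. For an assumed true risk p = 10%:

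- n = 10: 1 − 0.90^10 = 65% with full capture; 1 − 0.95^10 = 40% at half capture
- n = 8: 1 − 0.90^8 = 57% with full capture; 1 − 0.95^8 = 34% at half capture

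**The case against.** **The wording may be temporal.** The AE definition itself uses association in a temporal sense, and the sentence before the capture rule points to that definition. The rule might only be meant to separate research from routine care. This is possible, but the sentence does not say so, and under that reading its opening word would exclude almost nothing during treatment. The sentence would then be redundant and misleading.

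**The category for unrelated events has a use even under a strict reading.** The causality section concerns the study drug, while the research component also covers study procedures. An event caused by a blood draw would be captured and then classed as unrelated to drug. This stands, and it weakens the argument from that category alone. It does not remove the conflict with the definition, or with the instruction to weigh the underlying disease and concomitant therapy for each AE.

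**A reader might infer that worsening RLS or mood would go unseen.** The documents do not support that. The Schedule of Events has the RLS, augmentation, depression and suicidality scales at Visits 1 to 6, global impressions at those visits and every call, and diary review at each visit. What can be lost is such worsening as an AE with intensity and causality. Intercurrent illness is more exposed, although the medication review at each contact may leave a trace.

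**A reader might infer a bias in favour of ecopipam, or that the drug-placebo comparison is lost.** Neither follows. Capture is double-blind and the same rule applies in both periods, so recorded events stay comparable. Differential loss would need recognisable effects that hint at the treatment.

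**The schedule already has an AE query at each contact from Visit 1, and the example list is open-ended.** Both are true, but neither lifts the restriction on what is then recorded.

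**The sample is too small for firm safety conclusions anyway.** This stands: with 8 exposed subjects the limit is 31% even with complete capture. Tolerability also appears in the synopsis and not in Aim 1. It is still a stated purpose of the study.

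**Conclusion.** The contradiction is real and nothing in the protocol resolves it. If the capture sentence is followed as written, events thought unrelated to the research can be left out of the AE record before anyone assesses their cause. The expected result is under-counting in both periods and a weaker tolerability comparison, not necessarily a distortion towards one treatment.

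The size cannot be derived from the documents. The movement from 26% to 37% or 52% assumes that 70% or 50% of the events in question are captured and that all 10 subjects receive ecopipam. It applies to events staff might attribute elsewhere, not to recognised effects such as somnolence, which the rule would capture. The finding itself rests on the text and not on these figures. The sentence should be corrected because unrecorded events cannot be put back into the AE data at the analysis stage.

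**What to change.** Delete the capture sentence, with its examples, from Safety Monitoring of Subjects. In its place, state that every AE meeting the protocol's own definition is recorded at each scheduled visit and call, from first dose to the last call, irrespective of presumed cause and including worsening of RLS. State also that relationship to study drug is assessed after the event has been recorded and while treatment remains blinded.

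The cost is a change of wording and a few more AE lines for up to 10 subjects. No contact is added, because the Schedule of Events already includes an AE query at every visit and call from Visit 1 to the last call.
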